At the end of the Trial Phase, subjects will be assessed for pain intensity under optimal therapy parameters. Anterior-posterior (AP) and lateral X-ray imaging may be done at the end of the Trial Phase. The subject will be assessed for adverse events and medication usage.

Those who have a "successful Trial Phase" (defined as a 40% or greater pain reduction from Baseline in their back pain) will proceed to permanent implantation of a SCS system to evaluate the assigned therapy, and permanent implantation of the Intellis™ SCS system will be scheduled. A threshold of 40% for the Trial Phase was predetermined as the minimum pain reduction that warrants consideration of a permanent implant and an

opportunity to achieve a 50% pain reduction as defined in the Individual Subject Success criterion (see Section B.7.3.).)

Data from subjects who did not achieve 40% or greater pain reduction in back and do not receive permanent implantation will be carried forward toward the primary and secondary endpoints. These subjects will exit the study after being followed up for two weeks after explant of the leads to assess adverse events.

B.6.8. Permanent Device Implant (0-60 days from end of successful Trial Phase)

As described in section B.6.7, subjects who underwent a successful trial of the assigned SCS therapy and who agreed to continue into the next stage of the study will proceed to permanent implantation stage.

Permanent percutaneous leads will be placed in the epidural space at a vertebral level based on the subject's pain condition and pain pattern as described in the Intellis™ Physician Implant Manual. The INS will be implanted by a trained physician according to standard practice and following the Physician Implant Manual for the device. Anterior-posterior (AP) and lateral X-ray imaging will be obtained. Standard practice of a study site for prophylactic pre-surgery antibiotics and post-surgery pain medications will be followed). Subjects will be assessed for adverse events and medication usage.

B.6.9. Device Activation (0-14 days following Permanent Implant)

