If there are no ongoing study related adverse events, the subject will complete the study at this visit. In situations where there is an ongoing study related adverse event, subjects will be followed until resolution of that adverse event or determination that the subject's condition is stable, at which point the Study Completion Clinical Research Form (eCRF) should be completed.

Beyond the 12 month visit, there will be no additional scheduled follow-up visits in the study. Following the last scheduled study visit, subjects will be followed by the Investigator at regular intervals, as dictated by standard of care at each site, in order to facilitate pain management, stimulation adjustments, possible revisions and/or replacements of neurostimulation components. Any additional non-study related monitoring of the subject will be the responsibility of the subject's personal physician, as dictated by reasonable medical care.

B.6.17 Other Assessments and Information

At any time during the study, if lead migration is suspected, the subject may have additional AP and lateral X-rays taken to confirm the new lead position in order to aid the Investigator in determining a course of action.

Paresthesia testing may also be performed to assess lead location and therapy coverage of pain areas. Programming adjustments may be made based on patient feedback following assessment.

Additional information on Medication Usage:

- The investigator will instruct all subjects to take the Baseline doses of pain medication until the 3-Month Visit. However, after Device Activation Visit, the Investigator may reduce the dose of pain medication if the subject is benefitting greatly from SCS and not benefitting from Baseline dose pain medication.
 - Subjects should not fluctuate medication usage nor dosages even if the dose is at or below Baseline doses. The research coordinator or investigator should instruct all subjects to maintain stable dosing of medication for at least two weeks prior to scheduled follow-up visits.

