- Acetaminophen, NSAIDs or other pain medications (new prescriptions or greater than Baseline doses) may only be taken for an acute condition and for a limited duration. For each type of pain medication, dosing should not exceed the maximum daily dosage recommended by the manufacturer and usage should not continue beyond 5 days. Should acute pain medication usage coincide with a follow-up visit, the visit will be postponed until two weeks after acute pain medication usage has been stopped.
- Following trial and permanent implants, the clinical site's standard practice for prophylactic pre-surgery antibiotics and post-surgery pain medications will be followed. Investigators will instruct subjects not to change usage of any other concomitant pain medications.

B.6.18. Device Explant

At any time during the study, a subject may elect to withdraw from the study and have the SCS device system explanted. Additionally, an Investigator may elect to explant a device due to an adverse event.

The Investigator must follow the appropriate guidelines set forth by the Medtronic for returning the explanted device and/or lead(s) as well as the accessories (charger, patient remote control).

B.6.19. Early Subject Withdrawal

Although efforts will be made by Investigators and study staff to encourage subjects to remain enrolled in the study, subjects may withdraw early from the study for a number of reasons, including but not limited to:

- Failure of SCS Trial Phase
- Subject request
- Investigator request
- Subject lost to follow-up
- Subject's death
- Adverse events (e.g., intolerable adverse event occurrence that forces subject to stop participation in the study)

If a subject is considering withdrawing from the study due to unsatisfactory effectiveness of the assigned treatment, the Investigator will make attempts to improve therapy during a study visit. When a subject is withdrawn early from the study, a Study Termination eCRF will be completed describing the reason for discontinuation. Study staff will contact subjects to remind them about their scheduled visits and make sufficient efforts to locate a subject that is not responding to a contact call. In situations where study withdrawal is due to an adverse event, subjects will be followed until resolution of the adverse event or determination that the adverse event is not likely to change.

B.6.20. Study Completion

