B.7. Study Endpoints

B.7.1. Definition of Analysis Populations

- Modified Intent to Treat (mITT): All successfully randomized subjects who complete the Trial Phase.
- Intent-to-Treat (ITT): All successfully randomized subjects who met all the enrollment criteria.
- Per-Protocol (PP): All subjects who received a permanent device implant and contributed their data to the 3-month endpoint without any major protocol deviations or adverse events (that would render their data unevaluable).

The primary analysis of the primary and secondary endpoints will be performed on the mITT population. Supportive analyses will be performed for the Intent-to-Treat and Per-Protocol population.

For analyses incorporating crossover data (i.e. data gathered in the post 6-month periods), analyses will be based on the mITT population with treatment group defined by the treatment status at the corresponding time point to capture the impact of crossover. Additional sensitivity analyses censoring data post-crossover will be performed to examine the impact of crossover.

B.7.2. Effectiveness Assessment Definitions

- Primary Effectiveness Assessment: For subjects who have a successful Trial Phase and receive a permanent implant, the Primary Efficacy Assessment occurs at the follow up visit 3 months after Device Activation. For subjects who do not have a successful Trial Phase (based on subject's pain score) or subjects who do not want a permanent device implant due to insufficient pain relief (based on subject's discontinuation reason), the Primary Efficacy Assessment occurs at the end of the Trial Phase.

B.7.3. Primary Endpoint

Pain rating on the 10 cm Visual Analog Scale is considered the primary outcome measure. VAS is the most widely used outcome measure in assessing pain due to its documented reliability and validity, ease in administration, and minimal training requirements for the administrator.

- ***Individual Responder:*** A decrease in back pain VAS by at least 50% at 3 months after Permanent Device Activation as compared with Baseline. All subjects must be using the assigned programming parameters. If a subject is switched to a programming parameter that is not considered to be DTM-SCS nor Conventional SCS programming the subject will be counted as a non-responder for the following follow-up visit if one of the two following conditions exist:

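### Two exits that involve a removal, refusal of implant after a successful trial and elective system explant, have no stated adverse event contact afterwards

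*Combined protocol and SAP*

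**What the plan says.** **Trial phase.** B.6.7 describes one group, "Data from subjects who did not achieve 40% or greater pain reduction in back and do not receive permanent implantation", and says of it: "These subjects will exit the study after being followed up for two weeks after explant of the leads to assess adverse events".

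**Going on to implant.** Under B.6.8 the implant stage is for "subjects who underwent a successful trial of the assigned SCS therapy and who agreed to continue into the next stage of the study". Reaching 40% relief is therefore not enough; the subject must also agree. B.7.2 recognises refusals as a group separate from failed trials, namely "subjects who do not want a permanent device implant due to insufficient pain relief", but uses the group only to set when the primary assessment takes place.

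**After implant.** B.6.18 opens with: "At any time during the study, a subject may elect to withdraw from the study and have the SCS device system explanted". It then adds: "Additionally, an Investigator may elect to explant a device due to an adverse event". The rest of the section concerns return of the hardware to the manufacturer.

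**Withdrawal and completion.** B.6.19 requires a termination form for early withdrawals and provides: "In situations where study withdrawal is due to an adverse event, subjects will be followed until resolution of the adverse event". B.6.16, on the 12-month visit, provides: "In situations where there is an ongoing study related adverse event, subjects will be followed until resolution of that adverse event". B.6.20 and B.6.21 make similar provision at study completion and at early termination of the study.

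**The concern.** In B.6.7 the sponsor accepts that a removal should be followed by a check for new AEs, and sets the interval at two weeks. As written, that check depends on the pain score and not on the procedure. A subject with 35% relief whose trial leads are taken out is followed for two weeks. A subject with 45% relief who refuses the implant and has the same leads taken out has no stated contact. Nor does a subject who leaves later and has the whole implanted system removed, leads and neurostimulator together.

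What is at stake is the completeness of safety capture. Characterising the safety of the test programming is part of the secondary objectives (B.2), and safety is to be reported descriptively (B.8.3). Section C.1 lists infection, cerebrospinal fluid leakage, and epidural bleeding, hematoma or paralysis among the risks of the procedures. If such an event first appears after one of these removals, the study record depends on the site happening to hear of it.

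**Working it through.** No arithmetic applies. The check sets each AE provision against the two exits and asks whether it schedules a contact after the removal that would detect a new event.

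1. **B.6.7, two-week rule.** Its two conditions are relief under 40% and no permanent implant. A decliner at 40% or more fails the first. An explanted subject fails the second, and the rule concerns trial leads only. Neither exit is covered.

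2. **B.6.8 and B.7.2, decliners.** B.6.8 makes it possible to pass the trial and not proceed. B.7.2 assigns those who refuse for insufficient relief a primary assessment at the end of the trial phase, with nothing on safety. The last AE check stated for a decliner is the end-of-trial assessment in B.6.7. The plan does not say when a decliner exits relative to lead removal.

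3. **B.6.18, elective explant.** The first sentence joins withdrawal and explant. Only device-return instructions follow. No visit or call is stated.

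4. **B.6.19, early withdrawal.** Follow-up is triggered when an AE is the reason for withdrawal. An elective withdrawal for another reason does not trigger it. The termination form has no stated timing relative to removal.

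5. **B.6.16, B.6.20 and B.6.21.** Each extends follow-up for an AE that is ongoing at the 12-month visit, at completion or at study termination. None looks for an event that has not yet appeared.

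6. **B.8.3.2, AE window.** AEs are captured from enrollment to study completion. This defines a period, not a contact, and for an elective explant the withdrawal that ends participation is tied to the removal itself.

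7. **B.6.10, unscheduled visits.** These are optional and take place during the study.

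8. **E.3, serious AE reporting.** The 48-hour clock starts when the investigator learns of a study-related event. It does not create the means of learning.

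9. **Table 1.** There is no post-removal column, even for the existing two-week rule. The footnote allowing study completion at the end of the trial phase applies only to unsuccessful trials.

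For both exits the result is the same: no provision schedules an AE contact after the removal.

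**The case against.** The strongest reply is that this is a post-market study of an approved device, so reliance on routine care after exit may be deliberate. B.6.14 passes a subject who is withdrawn for gross lead migration to the pain physician as an ordinary commercial patient, and E.1.2 refers in general terms to reporting and following up study-related AEs. Routine care may well protect the patient. It does not ensure that the event reaches the study database, and neither passage sets a contact.

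For decliners there is a further point. Nothing in the plan ends their participation before the leads come out, so the AE window and unscheduled visits may still apply at that time. That stands: for this group the plan leaves the exit point open, and no loss of events has been shown. The consent form (Appendix A) is not in the copy reviewed and might contain contact terms.

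Three stronger readings are tempting, and the documents do not support them.

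- A reader might infer that explants prompted by an AE are also a gap. The second sentence of B.6.18 does not say that such an explant ends participation. A subject who stays enrolled keeps the scheduled visits, and one who withdraws because of the AE remains in follow-up under B.6.19.
- A reader might take the planned loss of about 35 subjects (135 randomized less 100 completing) as an upper limit on uncovered removals. B.5.5 counts subjects who completed the primary assessment, and B.7.2 places that assessment at the end of the trial for those who decline because of insufficient relief. On that reading they are among the 100. B.5.5.2 can be read the other way. Explants after month 3 are not projected at all.
- A reader might treat the one epidural abscess in the earlier trial-stimulation study, which 20 subjects completed (B.1), as a rate of missed events. Its timing relative to lead removal is not given, so it is not such a rate.

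**Conclusion.** The concern holds as a minor gap in safety capture. Followed as written, the plan has no post-removal AE contact for subjects who decline the implant at 40% relief or more, or for subjects who electively withdraw and have the system explanted. New procedure-related events after these removals may go unrecorded.

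Its size cannot be stated. The documents give no count of either exit and no frequency of events first seen after removal. Confidence is high that the text is silent; nothing here shows that events will be lost. The conclusion assumes that no contact is prescribed in material outside the copy reviewed. The primary non-inferiority test, its alpha and its power do not depend on this point.

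**What to change.** State in B.6.7, B.6.18 and B.6.19 that every subject who exits the study with removal of trial leads or of the implanted system will be phoned two weeks after the removal to ask about new AEs, unless the subject refuses or cannot be reached, in which case the reason is recorded. The completion or termination form is filled in after the call or after the reason is recorded. Subjects withdrawn because of an AE continue under the existing B.6.19 rule. Add the contact to Table 1, which would also bring the table into line with the existing two-week rule.

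The cost is wording in three sections, one table entry and one call per exit of this kind; subjects under 40% relief already have the follow-up. B.9.1 accepts the phone as a way to confirm AEs at remote study visits, so the mode is familiar, although that passage does not itself provide for contact after exit. The downside is that reported AE counts may rise slightly.

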Exclusion Criteria	
A subject must NOT MEET ANY of the following exclusion criteria:
 
 1. Had previous lumbar spinal surgery (e.g., lumbar fusion, discectomy, laminectomy, laminotomy) 2. Has a medical, anatomical, and/or psychosocial condition that is contraindicated for commercially available Intellis™ SCS systems as determined by the Investigator 3. Has a diagnosed back condition with inflammatory causes of back pain (e.g., onset of severe pain with activity), serious spinal pathology and/or neurological disorders, as determined by the Investigator 4. Be concurrently participating in another clinical study 5. Has an existing active implanted device such as a pacemaker, another SCS unit, peripheral nerve stimulator, and/or drug delivery pump, etc. 6. Has a pain in other area(s) and/or medical condition requiring the regular use of significant pain medications that could interfere with accurate pain reporting, and/or confound evaluation of study endpoints, as determined by the Investigator 7. Has mechanical spine instability as determined by the Investigator 8. Has undergone, within 30 days prior to enrollment, an interventional procedure and/or surgery to treat back and/or leg pain, which is providing significant pain relief 9. Has unresolved major issues of secondary gain (e.g., social, financial, legal), as determined by the investigator

	
10. Be involved in an injury claim under current litigation or has a pending or approved worker's compensation claim
 
11. Be pregnant (determined by urine testing unless female subject is surgically sterile or post-menopausal. If female, sexually active, and childbearing age, subject must be willing to use a reliable form of birth control.)

Primary Endpoint	The primary efficacy endpoint is the percentage of randomized subjects who respond (a decrease in back pain VAS by at least 50% compared to baseline) to SCS therapy at 3 months (non-inferiority analysis). Subjects who do not have a successful Trial Phase are considered failures (non-responders) toward the primary endpoint.

Table of Contents

CLINICAL INVESTIGATIONAL PLAN	1
Study Synopsis.....	2
A. Purpose.....	7
A.1. Study Device	7
A.2. Purpose of the Investigation.....	7
A.3. Study Size	7
A.4. Duration of the Investigation	8
B. Protocol	8
B.1. Rationale for Study.....	8
B.2. Study Objectives	10
B.3. Selection of Study Population	10
B.3.1. Study Population	10
B.3.2. Inclusion Criteria.....	10

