E. Administrative Procedures.....	40
E.1. Monitoring.....	40
E.1.1. Study Clinical Monitor	40
E.1.2. Monitoring Procedures	40
E.2. Data Quality Assurance	41
E.3. Study Conduct	41
E.4. Informed Consent Materials	42
E.5 Investigators and Institutions.....	42
E.6. Amendments and Deviations.....	42
E.7. Additional Record and Reports	43
F. Appendices	44
G. References.....	45

A. Purpose

A.1. Study Device

The Intellis™ neurostimulator is a commercially available implantable component of a Spinal Cord Stimulation (SCS) device system manufactured by Medtronic (Minneapolis, MN). The system is indicated for spinal cord stimulation (SCS) as an aid in the management of chronic, intractable pain of the trunk and/or limbs-including unilateral or bilateral pain associated with conditions, including Degenerative Disk Disease (DDD)/herniated disk pain refractory to surgical and conservative interventions. It is designed to deliver electrical stimulation to the spinal cord using arrays of electrodes (also called leads) placed in the dorsal epidural space. The study will use commercially available Intellis™ neurostimulator and compatible SCS system components from Medtronic in accordance to the approved FDA indications and labeling. Section D of this Investigational Plan provides detailed description of Intellis™ neurostimulator.

A.2. Purpose of the Investigation

The purpose of this post-market study is to evaluate the effects of Differential Target Multiplex SCS (DTM™SCS) programs in subjects with chronic, intractable pain of the trunk with or without lower limb pain associated with the following conditions: Degenerative Disk Disease (DDD)/herniated disk refractory to conservative and not a candidate for surgical interventions, in the absence of previous back surgery. Differential Target Multiplexed SCS (DTM-SCS) programming approach relies on stimulation parameters that will be set to levels that span above the perception threshold, yet well below the levels that could cause uncomfortable paresthesia. This study is a post market, open-label, multi-center, prospective, randomized, controlled clinical trial that evaluates the treatment outcomes resulting from DTM-SCS programming approach and Conventional SCS programming approach. Both programming approaches will be discussed in section B.1 of this Investigational Plan.

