8. Be willing to not increase pain medications from baseline through the 3-Month Visit
9. Be willing and able to comply with study-related requirements, procedures, and visits

B.3.3. Exclusion Criteria

In order to participate in the study, a subject must *NOT* MEET ANY of the following exclusion criteria:

1. Had a previous spinal surgery (e.g., lumbar fusion, discectomy, laminectomy, laminotomy)
2. Has a medical, anatomical, and/or psychosocial condition that is contraindicated for commercially available Intellis™ SCS systems as determined by the Investigator
3. Has a diagnosed back condition with inflammatory causes of back pain (e.g., onset of severe pain with activity), serious spinal pathology and/or neurological disorders as determined by the Investigator
4. Be concurrently participating in another clinical study
5. Has an existing active implanted device such as a pacemaker, another SCS unit, peripheral nerve stimulator, and/or drug delivery pump, etc.
6. Has pain in other area(s) and/or medical condition requiring the regular use of significant pain medications that could interfere with accurate pain reporting, study procedures, and/or confound evaluation of study endpoints, as determined by the Investigator
7. Has mechanical spine instability as determined by the Investigator
8. Has undergone, within 30 days prior to enrollment, an interventional procedure and/or surgery to treat back and/or leg pain, which is providing significant pain relief
9. Has unresolved major issues of secondary gain (e.g., social, financial, legal), as determined by the investigator
10. Be involved in an injury claim under current litigation or has a pending or approved worker's compensation claim
11. Be pregnant (determined by urine testing unless female subject is surgically sterile or post-menopausal. If female, sexually active, and childbearing age, subject must be willing to use a reliable form of birth control.)

B.4. Treatment Groups

Subjects meeting the study entrance criteria will be randomized to one of two study treatment groups in a 1:1 ratio:

- Control Treatment Group: Conventional SCS programming approach
 - Stimulation parameters in the 40-250 Hz frequency range will be trialed according to standard practice as described in the Intellis™ labeling/manuals
 - If frequency parameter above 250 Hz is used during the study, the subject will be counted as failure towards Conventional SCS programming approach but will continue to permanent implant.

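### The supportive ITT set carries an eligibility condition, so none of the planned analysis sets is defined to contain everyone randomised

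*Combined protocol and SAP*

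**What the plan says.** Section B.7.1 defines three sets.

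- Intent-to-Treat: "All successfully randomized subjects who met all the enrollment criteria".
- "Modified Intent to Treat (mITT): All successfully randomized subjects who complete the Trial Phase". This set has no eligibility condition.
- Per-Protocol: permanent implant, data at the 3-month endpoint, and no major protocol deviation or adverse event that would make the data unevaluable.

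On their roles: "The primary analysis of the primary and secondary endpoints will be performed on the mITT population", and "Supportive analyses will be performed for the Intent-to-Treat and Per-Protocol population".

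The synopsis states the primary endpoint as a percentage of randomised subjects. Sections B.7.3 and B.8.2 tie study success to the primary non-inferiority test alone.

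On prior surgery, exclusion 1 in the synopsis reads "Had previous lumbar spinal surgery (e.g., lumbar fusion, discectomy, laminectomy, laminotomy", and exclusion 1 in B.3.3 reads "Had a previous spinal surgery (e.g., lumbar fusion, discectomy, laminectomy, laminotomy". The title and B.2 speak of spine surgery. Section A.2 has "in the absence of previous back surgery".

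**The concern.** An ITT set should be fixed by randomisation alone. Here membership also depends on whether a subject met the entry criteria, and B.7.1 does not say who decides this, when, or on what information. Subjects, implanting physicians and site staff all know the assignment (B.5.4). Five exclusions in B.3.3 (items 2, 3, 6, 7 and 9) are left to the investigator's determination. A ruling made after randomisation could therefore be made with the arm, and possibly the pain result, in view.

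The supportive ITT analysis also has a job to do. The primary set leaves out randomised subjects who do not complete the Trial Phase, and ITT is the only planned set that brings them back. If ITT drops a different group at the same time, the contrast between ITT and mITT reflects two exclusions rather than one.

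**Working it through.** **Who falls in which set, from B.7.1**

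| Randomised subject | ITT | mITT |
|---|---|---|
| Eligible, completed Trial Phase | yes | yes |
| Eligible, did not complete | yes | no |
| Ineligible, completed | no | yes |
| Ineligible, did not complete | no | no |

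The third row shows that mITT is not nested in ITT. The fourth row is in no set, because Per-Protocol needs an implant. Going from mITT to ITT adds row two and removes row three.

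**The plan's own figures (B.5.5.1, B.5.5.2)**

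Inputs: responder rates 70% and 50%, margin 10 points, one-sided alpha 0.05, 50 per arm, attrition of 25% after and 46% before randomisation.

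- Farrington-Manning power = Φ[(0.70 − 0.50 + 0.10 − 1.645·s0)/s1].
- s1 = √(0.70·0.30/50 + 0.50·0.50/50) = 0.0959.
- s0 uses the restricted estimates 0.544 and 0.644: √(0.544·0.456/50 + 0.644·0.356/50) = 0.0977.
- Power = Φ[(0.30 − 0.1607)/0.0959] = Φ(1.452) = 92.7%, in line with the stated 90% or greater.
- 100/(1 − 0.25) = 133.3, rounded up to 134, against about 135 stated. 135/(1 − 0.46) = 250, as stated.

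**Size of the ITT set and power**

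The documents give no ineligible share. Assuming 0%, 2%, 5% or 10% of 135 gives ITT totals of 135, 132, 128 or 122. Power at the design rates is then 97.5%, 97.2%, 96.9% or 96.2%. Power is not the issue.

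**Possible shift in the rates (assumed numbers)**

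Take 67 per arm, about half of 135. Rates near the planning values are 47/67 = 70.1% (test) and 33/67 = 49.3% (control), a difference of 14/67 = 20.9 points. Remove k non-responders as ineligible.

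| Removed from | k = 0 | k = 3 | k = 5 | Change in difference (k = 3; k = 5) |
|---|---|---|---|---|
| Test only | 47/67 = 70.1% | 47/64 = 73.4% | 47/62 = 75.8% | +3.3; +5.7 points |
| Control only | 33/67 = 49.3% | 33/64 = 51.6% | 33/62 = 53.2% | −2.3; −4.0 points |
| Both arms, k each | 14/67 = 20.9 points | 14/64 = 21.9 points | 14/62 = 22.6 points | +1.0; +1.7 points |

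The first two rows show the arm's rate and the third shows the difference. Three to five subjects are 4.5% to 7.5% of an arm of 67. Removal from one arm only, all of them non-responders, is the extreme case. With no ineligible subject randomised, every change is zero.

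**Prior surgery**

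The two lists give the same examples and differ only in the word lumbar. A person whose only operation was elsewhere on the spine is not excluded by the synopsis list but is excluded by B.3.3.

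**The case against.** The best defence is that the clause may never operate. Records go to a sponsor-designated physician for pre-screening (B.6.2), subjects without confirmed eligibility are discontinued before Baseline (B.6.3), and only qualifying subjects are randomised (B.6.5). On that path the clause may simply describe who reaches randomisation. No section sets out an eligibility review after randomisation, so a reader who infers that the plan schedules such removals goes further than the text. What stands is that the literal wording permits them and sets no rule for them.

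A reader might also infer that the primary result is compromised. It is not: mITT has no eligibility condition, and success does not depend on ITT. Nor is the supportive analysis useless. As written, ITT still restores eligible subjects who did not complete the Trial Phase, so it can show most of what the mITT restriction did.

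Finally, it is tempting to treat prior surgery as the criterion that decides ITT membership. It is one of 20 (9 inclusion, 11 exclusion). The wording difference touches only people with non-lumbar surgery alone. It applies before randomisation and so to both arms alike, and B.3.3 agrees with the title and B.2. It is a separate editorial matter, though the documents do not say which list governs.

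**Conclusion.** The point holds as a minor one. By its wording, the set labelled ITT is not the set of all randomised subjects, no other set fills that gap, and the sets are not nested. In an open-label trial with investigator-judged exclusions, this leaves room for exclusion after randomisation with arm and outcome known.

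The consequence is confined to a supportive analysis. Its size is unknown and may be zero. The worst-case shifts rest on assumed counts, one-arm removal and only non-responders removed; their direction depends on the arm. They mark an outer range and are not a forecast of bias.

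**What to change.** In B.7.1, define ITT as all randomised subjects, analysed in the arm to which they were randomised, and delete the closing eligibility clause. Record ineligibility found after randomisation as a protocol deviation and deal with it through the Per-Protocol set's major-deviation rule, stating there that eligibility violations are considered under that rule. If no ineligible subject is ever randomised, the change alters nothing.

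Separately, the sponsor should reconcile exclusion 1 between the synopsis and B.3.3 so that both lists describe one population. Which wording applies is for the sponsor to state.

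Both are text changes. They need no new data and leave the sample size and the primary analysis as they are.
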